Recent literature from the Human Microbiome Project has shown there are unique microbial signatures specific to healthy and acne disease states (Fitz-Gibbon et al. 2013), (Tomida et al. 2013). Subsequent literature discovered a repressor in the porphyrin pathway in health-associated strains resulting in significantly lower porphyrin production (Johnson et al. 2016). Porphyrin is a known inflammatory mediator in acne pathogenesis (Kang et al. 2015). Porphyrin levels inversely correlate with therapeutic improvement in acne. (Richter et al. 2016). Additional papers have highlighted other virulent factors such as the pIMPLE plasmid that may be associated with acne pathogenesis and were found to be more common in disease-associated strains (Kasimatis et al. 2013).

From this data, we hypothesize that by eliminating resident disease-associated bacterial strains and replacing them with a health-associated *P. acnes* transplant, we may be able to improve, mitigate, treat, or prevent acne flares. We aim to test this in an initial Phase I evaluating the safety, tolerability, and clinical impact that a single dose application of NB01 has on adult subjects with moderate acne.

This initial study will be a Phase Ib single center open label dose escalation study using a single dose application with monitoring over 28 days on 10 subjects at 2 different concentrations (lower bound and upper bound). If we meet the safety criteria of this initial study, we plan to expand the IND research to a Phase Ib multi-dosed study. All subjects will be pre-treated with a daily 5.0% BPO gel (<https://www.perrigo.com/business/product.aspx?ID=88&let=B> Perrigo 5% BP Aqueous Gel) to decrease their resident microbiome bacterial load in preparation for transplantation and successful repopulation with a healthy microbiome.

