3 OBJECTIVES AND ENDPOINTS

OBJECTIVES	ENDPOINTS	JUSTIFICATION FOR ENDPOINTS
Primary		

 Determine the safety and tolerability of a singly applied NB01 Define engraftment of a singly applied topical NB01 Dose schedule determination based on engraftment 	
Safety Assessments:
 
 Skin Dryness Skin Peeling Irritant/Contact dermatitis Hyperpigmentation Ocular Toxicity Mucosal Toxicity Skin erythema Assessment of Disease Status 
Efficacy Assessments: Engraftment is defined as deoR/PanBac>40% and Cas5/PanBac>40%. Disease associated bacteria are typically deoR, Cas5 negative (Kang et al, 2016), therefore, ratios are expected to be low <10% in acne subjects. The NB01 strain as measured with our TaqMan assays is approximately 100% deoR/PanBac and Cas5/PanBac, so we expect the ratio to increase with successful engraftment. This will help to determine dosing regimen/schedule for multi-dosed trials where the drug will be applied in a frequency to ensure that product levels remain above these parameters. For example, if deoR/PanBac drops to <40% at or before 6 hours then the application will be twice daily (BID); every (Q) 12 hours.
	Disease exacerbation along with erythema, dryness, pigmentation irritant/contact dermatitis, mucosal and ocular toxicity are commonly tested safety endpoints in topical dermatologic trials.
Secondary		
To evaluate clinical efficacy using IGA and acne lesion counts of a singly applied NB01	IGA and acne lesion count	IGA and acne lesion counts are conventional measurements for assessing efficacy in acne trials
Tertiary/Exploratory		
To evaluate biomarkers of	
 Porphyryn and sebum levels 	Porphyryn is a known

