We aim to test this in a Phase Ib single application study evaluating the safety, tolerability, and clinical impact that a single application of NB01 has on adult subjects with moderate acne. We want to profile the change in microbiome over the course of therapy to determine if exogenously delivered bacteria can populate the skin (engraftment) and cause a shift in the microbiome safely and subsequently impact acne biomarkers (porphyrin) that may correlate with clinical disease. Health-associated *P. acnes* contain both deoR and Cas5, thus the ratios of deoR/PanBac and Cas5/PanBac is approximately 1 in our formulation. Disease associated *P. acnes* typically lack deoR and Cas 5 (Kang et al, 2016) leading to a deoR/PanBac <10% on acne individuals. We expect an upwards shift in deoR/PanBac and Cas5/Panbac with the application of our strains to acne subjects. Thus, engraftment is defined as deoR/PanBac>40% and Cas5/PanBac>40%. This will help to determine dosing regimen/schedule for multi-dosed trials where the drug will be applied in a frequency to ensure that product levels remain above these parameters. For example, if deoR/PanBac drops to <40% at or before 6 hours then the application will be BID (Q12 hours). Disease-associated strains, in contrast, typically lack deoR and Cas4, but contain transposase2 (TPase2). Subjects will also be profiled with TPase2/PanBac ratios to determine how the pathogenic strain profiles are impacted over time with application of drug, and if there are certain profiles that increase or decrease likelihood of successful engraftment.

Engraftment measurements would be more challenging to obtain in healthy individuals in which we would be trying to replace a healthy microbiome with a healthy microbiome. Our product is low risk, using bacteria native not only to human skin, but to the pilosebaceous units of the face, and *P. acnes* makes up 90% of the bacteria on the skin in both diseased and healthy individuals (Fitz-Gibbon et al. 2013).

We intend for this therapy to eventually be used in all ages of acne subjects ranging from 13-40, and all disease severities as either monotherapy for mild to mild/moderate acne and as an adjuvant therapy for moderate to severe acne at all body sites, with special attention to facial involvement.

This approach is standard to acne therapy whereby mild disease will be treated with a monotherapy (i.e., 5.0% BPO) and moderate/severe disease will be treated with various combinatory regimens (topical

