6 STUDY INTERVENTION

6.1 STUDY INTERVENTION(S) ADMINISTRATION

6.1.1 DOSING AND ADMINISTRATION

There will be a single application of NB01, at 1 of 2 dose cohorts, administered to approximately 10 subjects:

Once a subject has completed BPO pre-treatment (with an in-home patient e-diary) and been enrolled into the trial, the subject will provide a post-BPO sample immediately prior to receiving their application of NB01 (hereafter referred to as “study drug”). The PI will apply a single dose of NB01 at one of two strengths to each subject at time point 0 hours (0H):

- Cohort 1: Initially, 5 subjects will be enrolled to receive a single topical application of NB01 at 10^5 CFU/cm² to 50 cm² of facial skin covering the nose and cheek. The lower-bound dose determined using the average range of normal bacterial concentration for facial skin (10^5 CFU/cm²).
- Cohort 2: If there are less than 2 DLTs in Cohort 1, then 5 subjects will have a single topical application of NB01 at 10^6 CFU/cm² to 50 cm² of facial skin covering the nose and cheek. The upper-bound dose was determined by upper limit of normal bacterial concentration for facial skin (10^6 CFU/cm²).

Investigators applying the drug shall wash their hands and wear non-powdered nitrile gloves for application of study drug material. Subjects will wash their face with Cetaphil® right after the time point 0H engraftment sample procurement and just before the study drug application. Subjects will document their BID Cetaphil® washing for the remainder of the study.

See Study Assessments and Procedures, for details on pre-and post-visit requirements during the treatment period.

See the Pharmacy Manual for additional study drug handling and management details for this study.

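### TPase2/PanBac falls by dilution once NB01 is on the skin, so by itself it cannot show that disease-associated strains were displaced

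*Combined protocol and SAP*

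**What the plan says.** Section 4.2 describes TPase2 as a gene carried by disease-associated strains, in contrast to the deoR- and Cas5-positive health-associated ones. It gives TPase2/PanBac two uses. The first is the drug's effect: "Subjects will also be profiled with TPase2/PanBac ratios to determine how the pathogenic strain profiles are impacted over time with application of drug". The second is to learn "if there are certain profiles that increase or decrease likelihood of successful engraftment".

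On the denominator, the endpoint table in section 3 states: "The NB01 strain as measured with our TaqMan assays is approximately 100% deoR/PanBac and Cas5/PanBac". Section 4.2 repeats that "the ratios of deoR/PanBac and Cas5/PanBac is approximately 1 in our formulation". Engraftment is defined as both ratios above 40%, from an expected baseline below 10%.

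Section 6.1.1 gives Cohort 1 a "single topical application of NB01 at 10^5 CFU/cm² to 50 cm²" and Cohort 2 a "single topical application of NB01 at 10^6 CFU/cm² to 50 cm²". Section 4.3 puts normal facial bacterial density at 10^4 to 10^7 CFU/cm². Section 2.1 says benzoyl peroxide (BPO) is given beforehand "to decrease their resident microbiome bacterial load in preparation for transplantation".

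TPase2 does not appear in the endpoint table of section 3 or in the statistical section 10. Neither mentions an absolute quantity of TPase2 or PanBac, or a denominator that leaves out the product. Section 6.3 describes an open-label, sequential design, and there is no vehicle arm.

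**The concern.** A ratio whose denominator includes the study product responds to the product being present as well as to anything the product does. If PanBac detects NB01 one for one and NB01 carries no TPase2, applying NB01 enlarges the denominator and leaves the numerator alone. TPase2/PanBac then drops at the first post-application swab with the disease-associated load unchanged, and rises again as product is lost.

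The trial's hypothesis is that disease-associated strains are removed and replaced by the transplant. The planned ratio looks the same under replacement and under mere addition. At equal resident load and recovery, addition also gives a larger fall at the higher dose, which could be taken for a dose response. Without a control arm or an absolute quantity, nothing in the plan tells the two explanations apart.

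**Working it through.** The plan states no expected value for TPase2/PanBac, so there is no figure to reproduce. The check is a mixing identity.

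**Inputs**
- T = resident TPase2 signal, held constant (no displacement).
- R = resident PanBac load. Section 4.3 gives 10^4 to 10^7 CFU/cm² for normal facial skin. The load after BPO is not given and could be lower.
- D = dose: 10^5 or 10^6 CFU/cm² (section 6.1.1).
- f = fraction of applied product still present and recovered by the swab. It is not given; values of 1, 0.1 and 0.01 are assumed.
- b = baseline deoR/PanBac: 0 to 10% (section 3 expects below 10%).
- Assumptions: NB01 has no TPase2; its deoR/PanBac is 1; resident and product bacteria give the same PanBac signal per CFU.

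**Step 1. Effect of deposition.** The ratio goes from T/R to T/(R + fD). The fraction retained is R/(R + fD), whatever the starting TPase2 share.

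**Step 2. At the protocol's own engraftment threshold.** Let x = fD/R. With no displacement, deoR/PanBac after application is (b + x)/(1 + x). Setting this to 0.40 gives x = (0.40 − b)/0.60, and the retained fraction is 1/(1 + x) = 0.60/(1 − b).
- b = 0: x = 0.667, retained 0.600, a fall of 40%.
- b = 0.05: x = 0.583, retained 0.632, a fall of 37%.
- b = 0.10: x = 0.500, retained 0.667, a fall of 33%.

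This result needs no assumed resident load, retention or recovery.

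**Step 3. By dose and resident load.** Fall in TPase2/PanBac with zero displacement, 100 × fD/(R + fD), Cohort 1 dose / Cohort 2 dose:

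| R (CFU/cm²) | f = 1 | f = 0.1 | f = 0.01 |
|---|---|---|---|
| 10^4 | 90.9% / 99.0% | 50.0% / 90.9% | 9.1% / 50.0% |
| 10^5 | 50.0% / 90.9% | 9.1% / 50.0% | 1.0% / 9.1% |
| 10^6 | 9.1% / 50.0% | 1.0% / 9.1% | 0.1% / 1.0% |
| 10^7 | 1.0% / 9.1% | 0.1% / 1.0% | 0.0% / 0.1% |

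The fall is larger at the higher dose in every row. A lower resident load, which is the purpose of BPO, moves a subject up the table.

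**Step 4. Would a product-free denominator solve it?** TPase2/(PanBac − deoR) is unaffected by deposition only if NB01's deoR/PanBac is exactly 1, and the protocol says approximately. Take R = 10^4, D = 10^6, f = 1, and residents that are 80% TPase2-positive and deoR-negative (assumed), so T = 8,000 and PanBac = 1,010,000.
- NB01 ratio 0.99: deoR = 990,000, and 8,000/20,000 = 40% instead of 80%.
- NB01 ratio 0.95: deoR = 950,000, and 8,000/60,000 = 13%.
- NB01 ratio 1.01: the denominator is zero.

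Where product dominates the swab, this measure is badly biased too.

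**The case against.** The strongest reply is that the protocol speaks of profiling. A profile is a composition, a ratio to PanBac measures composition, and no passage says that a fall will be reported as elimination. This stands in part: the ratio is valid for relative composition. But section 4.2 also says it is to determine how the drug affects the pathogenic strains, and the hypothesis in the same section is their removal and replacement. The plan offers no other measure of that.

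The measure is also peripheral. It appears in the rationale only, no hypothesis is tested, and no escalation or stopping rule uses it. That stands, and it makes this a matter of interpretation and not of error rates.

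The size is uncertain too. With residents at 10^7, or with little product recovered, the fall is about 1% or less at the lower dose. Dilution lasts only while product or its DNA is on the sampled skin. It should therefore be largest at 6H and 24H, before washing resumes, and may have faded by Days 7 and 28.

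Three stronger readings are tempting, and the documents do not support them.
- A reader might infer that the ratio will also be used to judge BPO and would miss an even kill of all strains. Section 4.2 ties the ratio to application of drug, section 6.1.1 defines study drug as NB01, and nothing plans to assess BPO this way.
- A reader might infer that the search for predictors of engraftment is circular, because TPase2/PanBac and deoR/PanBac share one total. That holds only for post-application values. A likelihood of engraftment naturally refers to an earlier profile, and Screening and pre-application 0H swabs are already scheduled. The text just does not say so.
- A reader might infer that a false dose response is certain. The ordering assumes similar resident loads and recovery in both cohorts, which five non-randomised subjects per cohort cannot guarantee.

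**Conclusion.** The point holds as one of interpretation. While NB01 or its DNA is on the sampled skin, TPase2/PanBac falls through dilution alone. The fall is 33% to 40% for a subject who just reaches the 40% deoR/PanBac threshold by deposition, and larger above it. With full recovery it ranges from 91% to 1% at the lower dose and from 99% to 9% at the higher dose as residents go from 10^4 to 10^7 CFU/cm². With less recovery it shrinks towards zero.

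The conclusion rests on PanBac counting NB01, which follows from the protocol's own ratio of about 1, and on NB01 lacking TPase2. The second is implied by the contrast in section 4.2 but never stated, and the genotype described in section 2.2 does not mention TPase2. The sponsor should confirm it.

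The ratio can describe composition. By itself it cannot show that disease-associated strains were eliminated or that their load fell. It does not follow that the ratio should be dropped: it protects against differences in swab recovery, and the alternatives have faults of their own.

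**What to change.** In sections 4.2 and 10.4.1:
- Keep TPase2/PanBac and label it a measure of composition.
- Report log10 TPase2 and log10 PanBac quantity per swab beside it, each as change from the pre-application 0H sample.
- State that a fall in the ratio without a fall in TPase2 quantity will not be read as displacement.
- State that TPase2 values used as predictors of engraftment come from pre-application samples (Screening or 0H).
- State whether NB01 carries TPase2.
- If TPase2/(PanBac − deoR) is shown at all, limit it to a sensitivity measure in samples where deoR is well below PanBac.

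The cost is a few sentences and some descriptive output on targets the plan already intends to assay. It does require quantified TaqMan output for each target, which the protocol does not confirm. Quantity per swab also varies with swab recovery and with the facial quarter sampled at each time point (section 8.1), so a change in quantity in one subject should be read together with the change in PanBac and with the quarter swabbed.

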4.3 JUSTIFICATION FOR DOSE

P. acnes is normal, commensal bacteria on the facial skin and within the facial pilosebaceous units. *P. acnes* species make up around 90% of the bacterial species on the face, irrespective of health or disease states (Fitz-Gibbon et al. 2013), (Tomida et al. 2013). In administering our live microbiome transplant topically to the face, we are delivering our health-associated *P. acnes* strains directly into their native niche, enabling optimal engraftment and thereby any beneficial effect of restoring a microbiome population to a healthy profile.

Dose Justification:

- Lower-bound dose of 10^5 CFU/cm² determined using the average within the range of normal bacterial concentration for facial skin (10^4 - 10^7 CFU/cm²) (Kishishita et al. 1980), (Akaza et al. 2016), (Nakatsuji et al. 2017) (http://www.textbookofbacteriology.net/normalflora_3.html)
- Upper-bound dose of 10^6 CFU/cm² determined by using the upper limit of normal bacterial concentration for facial skin.

Further rationale to the study design of performing topical microbiome transplants with our dose can be extracted from the methods in (Nakatsuji et al. 2017) which studied autologous microbiome transplants of 10^5 CFU/cm² CoNS in atopic dermatitis subjects.

4.4 END OF STUDY DEFINITION

A participant is considered to have completed the study if he or she has completed all phases of the study including procedures for last visit, End of Study (EOS). See protocol section 8.1 for discontinuation criteria and visit procedure details.

5 STUDY POPULATION

Approximately 10 adult male and female subjects with moderate-noncyclical acne will be recruited for this study.

5.1 INCLUSION CRITERIA

Subjects must meet all the following inclusion criteria to be eligible for participation in the trial:

1. Ability to provide written informed e-consent.
2. Males and Females ages 18-40.
3. Acne severity: Moderate (Grade 3 on 5-point IGA scale and Moderate on an acne lesion count scale (Appendix B [Section 12.2], IGA and Lesion Count Acne Grading).
4. Acne treatment-free period (including topical or oral antibiotics, retinoids, laser therapy, topical dapsone, topical azelaic acid, facial peels, dermabrasion, sulfacetamide sulfur, and salicylic acid), of at least 3 weeks prior to e-consent (with the exception of BPO pre-treatment under this protocol).

5. Lesion count: A minimum of at least a total of 15 inflammatory lesions (papules plus pustules), with a minimum of 10 inflammatory lesions within the designated application area (cheek/nose).
6. Females with non-cyclical acne.
7. Females of childbearing potential willing to use adequate contraception (e.g., total abstinence, intrauterine device (IUD), barrier method with spermicide, surgical sterilization or surgically sterilized partner, Depo-Provera®, Norplant®, or NuvaRing® for the duration of the Screening Period and during study participation. All oral contraceptive and hormonal implants will need to have been initiated and on a stable dose for at least 3 months prior to the screening period. Women of childbearing potential are defined as any female who has experienced menarche and who is NOT permanently sterile or postmenopausal; postmenopausal is defined as 12 consecutive months with no menses without an alternative medical cause.
8. Male participants willing to use an acceptable method of contraception (e.g., total abstinence, barrier methods with spermicide, surgical sterilization or surgically sterilized partner) during study participation.

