1 PROTOCOL SUMMARY

1.1 SYNOPSIS

Title:	A Phase IB Dose Escalating Study of the Safety, Short-Term Engraftment and Action of a Singly Applied NB01 in Adults with Moderate Acne
Study Description:	
Acne vulgaris is a multifactorial disease caused by overgrowth of Propionibacterium acnes (P. acnes), impaction of hair follicles, excessive sebum production and hormonal dysregulation. Recent literature from the Human Microbiome Project has shown there are unique microbial signatures specific to healthy and acne disease states (Fitz-Gibbon et al. 2013), (Tomida et al. 2013). Subsequent literature discovered a repressor in the porphyrin pathway in health-associated strains resulting in significantly lower porphyrin production (Johnson et al. 2016). Porphyrin is a known inflammatory mediator in acne pathogenesis (Kang et al. 2015). Porphyrin levels inversely correlate with therapeutic improvement in acne (Richter et al. 2016). Additional papers have highlighted other virulent factors such as the pIMPLE plasmid that may be associated with acne pathogenesis and were found to be more common in disease-associated strains (Kasimatis et al. 2013).
 
From this data, we hypothesize that by eliminating resident disease-associated bacterial strains and replacing them with a health-associated P. acnes transplant, we may be able to improve, mitigate, treat clinical disease (acne) and prevent recurrences/flares of said disease. Instead of current approaches which focus on eliminating all bacteria from the skin, we aim to deliver healthy bacteria to restore the skin to a healthy state via this replacement therapy.
 
We aim to test this in a Phase Ib single application study evaluating the safety, tolerability, and clinical impact that a single application of a P. acnes transplant, hereafter referred to as NB01, has on adult subjects with moderate acne. We want to profile the change in microbiome over the course of therapy to determine if exogenously delivered bacteria can populate the skin (engraftment) and cause a shift in the microbiome safely and subsequently impact acne

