1.2 SCHEDULE OF EVENTS (SOE)

Schedule of Events (SOE) - Single Application (Phase IB): NB01-P1BSA

STUDY PERIOD ►	Baseline	Treatment						End of Study
STUDY DAY (± visit window) ►	Day -5	0H (+2 days)	6H (±2 hrs)	24H (±2 hrs)	48H (±2 hrs)	7 days (±1 day)	Unscheduled Visit ⁿ	28 days ^o (±3 days)
PROCEDURE ▼ TREATMENT DAY ►	Screening	Day 1 ^b	Day 1	Day 2	Day 3	Day 7	NA	Day 28/EOS
Eligibility Criteria Review ^a	X							
Electronic Informed Consent Process	X							
Medical History	X							
Concomitant Medication Review	X	X	X	X	X	X	X	X
Directed PE ^c	X	X					X	
Cheek Swab Engraftment Sample (TaqMan® Assay)	X ^f	X	X	X	X	X	X	X
Vital Signs ^{d, e}	X			X		X	X	X
Laboratory Assessment - CBC ^d	X						X	
Pregnancy Test (urine dipstick) ^g	X	X					X	X
BPO 5.0% gel application	X ^h							
Electronic Patient Diary	X ⁱ	X	X	X	X	X	X	X
Enrollment	X							
AE Assessment	X ^k	X ^j	X	X	X	X	X	X
Assess Porphyrin Levels (Pear 3D)	X	X	X	X	X	X	X	X
Sebum Production Measurement (Pear 3D)	X	X	X	X	X	X	X	X

Schedule of Events (SOE) - Single Application (Phase IB): NB01-P1BSA (concluded)

Skin pH measurement (Skin pH Meter)	X	X	X	X	X	X		X
Assess Follicular Engraftment via Bioré® Strip (TaqMan® Assay)	X			X				
Investigator Global Assessment (IGA)	X	X	X	X	X	X	X	X
Absolute Lesion Count	X	X	X	X	X	X	X	X
Photography (Pear 3D)	X	X	X	X	X	X	X	X
Facial Cetaphil® Washing	X ^{p,q}	X ^{l,m}	X	X	X	X	X	X
Investigator Assessment of Tolerability	X	X	X	X	X	X	X	X
Single NB01 application (by Investigator)		X						

Abbreviations: AE = Adverse Event; BID = Twice Daily; BPO = Benzoyl Peroxide; CBC = Complete Blood Counts; EOS = End of Study; PE = Physical Examination.

^a Includes confirmation of contraception use for the duration of Screening prior to first application and through study participation; Principal Investigator (PI) should assess subject eligibility after e-consent and prior to remaining screening period procedures.

^b All Day 1 baseline procedures must be completed prior to the PI application of NB01 at Time Point 0 (T0H).

^c Limited PE of face, chest, arms, back (relevant acne regions).

^d Vital signs and CBC assessed at Screening Visit, prior to initiation of BPO pre-treatment. Vital signs and CBC are only repeated if clinically warranted.

^e Blood pressure, heart rate, temperature.

^f Screening sample to be obtained prior to initiation of BPO pre-treatment.

^g Urine dipstick test, assessed locally.

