5.3 LIFESTYLE CONSIDERATIONS

Females of childbearing potential need to be willing to use adequate contraception (e.g., total abstinence, IUD, barrier method with spermicide, surgical sterilization or surgically sterilized partner, Depo-Provera®, Norplant®, or NuvaRing® for duration of the Screening period and during study participation. All oral contraceptive and hormonal implants will need to have been initiated and on a stable dose for at least 3 months prior to the screening period. Females must submit to a pregnancy test to ascertain that they are not pregnant before enrolling in the study.

Male participants must be willing to use an acceptable method of contraception (e.g., total abstinence, barrier methods with spermicide, surgical sterilization or surgically sterilized partner) during study participation.

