5.5 ENROLLMENT PROCEDURES AND TREATMENT ASSIGNMENT

The screening date will be defined as the date the subject signs the ICF. Subjects will be screened within 5 days (+2 days) of enrollment to determine eligibility for participation in the study. Screening laboratory results for hematology (Complete Blood Counts [CBC]) should be obtained from the local laboratory. Screening procedures (Section 8.1) will be performed and documented, at the end of which the clinical site will complete subject and visit information on the Enrollment Request Form (ERF) for Sponsor approval. Approved subjects who meet all inclusion criteria and none of the exclusion criteria may be enrolled into the trial.

It is the responsibility of the PI to ensure that subjects are eligible for the study prior to enrolling into the study. Subjects who do not enroll within the Screening Period will be screen failed. A subject will be considered enrolled once he or she has signed the ICF, met all inclusion/exclusion criteria, executed all screening visit measurements, including daily BPO therapy, and received Sponsor approval to participate.

This is an open-label study. Subjects will be assigned a unique Screening Number at the time of e-consent. Subjects who have met all eligibility criteria will initiate an at-home daily application of a 5.0% BPO gel treatment, and BID Cetaphil® wash and complete an electronic, in-home patient diary (e-diary). They will return to the clinic on Day 1 to perform baseline assessments. Day 1 is defined as the date the first application of NB01 will occur. All baseline tests and procedures must be completed prior to the application of the first dose of study drug on Day 1, time point 0H. Once eligibility is confirmed, subjects will be assigned a unique Subject ID number and be assigned to a cohort. Once a Subject ID has been assigned to a subject, it will not be reassigned to another subject.

Each on-study visit will be scheduled relative to Day 1 0H. Enrolled subjects will complete an in-home e-diary to capture at home Cetaphil® washing through the end of the study. Visits will follow the SOE table and protocol section 8.1. The ERF and additional details can be located in the Study Reference Manual for the trial.

Re-Screening of Subjects

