AEs occurring during the study will be recorded on an AE CRF. If AEs occur, the first concern will be the safety of the study participants.

Prior/Concomitant Therapies and Medications

At screening, all therapies and medication taken up to 2 months prior to the Screening Visit should be recorded on the eCRF. At each study visit, any therapies or medications taken by the subject since the last visit will be captured.

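### The 3-month contraceptive stability rule omits two accepted hormonal methods, so a subject may start an injectable or a ring at Screening, days before NB01

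*Combined protocol and SAP*

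**What the plan says.** Inclusion 7 (Section 5.1) asks women of childbearing potential to be "willing to use adequate contraception (e.g., total abstinence, intrauterine device (IUD), barrier method with spermicide", and continues the list of examples with sterilization and then "Depo-Provera®, Norplant®, or NuvaRing® for the duration of the Screening Period and during study participation". The next sentence adds the stability condition, counted back from Screening: "All oral contraceptive and hormonal implants will need to have been initiated and on a stable dose for at least 3 months prior". Section 5.3 repeats both parts, accepting "Depo-Provera®, Norplant®, or NuvaRing® for duration of the Screening period and during study participation" and limiting the 3-month condition to the same two routes.

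On checking, footnote a of the Schedule of Events (Section 1.2) describes the eligibility review this way: "Includes confirmation of contraception use for the duration of Screening prior to first application and through study participation". It asks for no duration of earlier use. On timing, Section 5.5 says "Subjects will be screened within 5 days (+2 days) of enrollment to determine eligibility".

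Exclusion 14 (Section 5.2) bars subjects who have foreign, prosthetic or implantable devices. It makes no exception for a contraceptive device.

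**The concern.** The Synopsis lists "excessive sebum production and hormonal dysregulation" among the causes of acne. Inclusion 6 restricts women to non-cyclical acne, and Inclusion 7 requires a settled dose for oral contraceptives and implants. The sponsor therefore already treats hormonal stability as something to protect, and the documents give no reason for leaving out the other two named hormonal products.

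IGA and lesion counts are the secondary endpoints and sebum is exploratory (Section 3). All are summarized before and after application, in an open-label sequential study with no concurrent control (Sections 6.3 and 10.1). If a subject starts a hormonal method in the same week as NB01, nothing in the design can separate the two for her.

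IGA also feeds the safety decision. A 1-point rise over the screening score within 7 days is a DLT criterion (Section 8.2.2), and fewer than 2 DLTs in Cohort 1 is a condition for considering Cohort 2 (Sections 4.1 and 6.1.1).

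**Working it through.** The protocol states no sample size, power or alpha figure that bears on this point, so the check is mainly one of text. That Depo-Provera is an injectable, NuvaRing a vaginal ring and Norplant an implant is ordinary product knowledge; the protocol does not say so.

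**1. Which accepted methods carry the 3-month condition (Inclusion 7 and 5.3)?**

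| Method | Accepted | 3-month stability required |
|---|---|---|
| Oral contraceptive | Implied by the stability sentence; not in the list of examples | Yes |
| Norplant | Yes | Yes |
| Depo-Provera | Yes | No |
| NuvaRing | Yes | No |
| IUD, type not stated | Yes | No; whether a hormonal type is meant is unclear |
| Abstinence, barrier with spermicide, sterilization | Yes | Not applicable |

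**2. Does another section close the gap?**

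- Inclusion 4 (acne treatment-free period) lists no hormonal agent.
- Section 6.3.1 restricts acne therapy, moisturizers, sunscreens, makeup and cleansers. It does not mention starting or switching a hormonal method.
- Footnote a of the Schedule of Events asks about use during Screening and on study only.
- Exclusion 20 (investigator's judgement on medical or psychiatric conditions and on drug or alcohol abuse) and the Sponsor's approval of each enrollment (Section 5.5) could stop such a subject, but neither states a rule on this.

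The gap therefore stands for Depo-Provera and NuvaRing.

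**3. How close to NB01 can the start be?** Screening runs 5 days, or up to 5 + 2 = 7. Ignoring the later visit windows, a subject who starts at Screening has used the method for:

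- 5 to 7 days at application;
- 5 + 7 = 12 to 7 + 7 = 14 days at the Day 7 safety assessment;
- 5 + 28 = 33 to 7 + 28 = 35 days at the last visit.

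A subject on an oral contraceptive or implant must have completed 3 months before Screening begins.

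**4. Weight of one subject.** 1/5 = 20% of a cohort and 1/10 = 10% of the trial. This is the share of any single subject; it does not measure bias.

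**5. The DLT route.** Inclusion 3 fixes entry at IGA Grade 3, so the criterion is met by a move to Grade 4, the top of the scale in Appendix B. Section 8.2.2 removes events due to the underlying disease or plainly explained by another cause. A newly started hormonal method makes that judgement harder in both directions: worsening might be charged to NB01 wrongly, or a true reaction might be put down to the contraceptive.

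**The case against.** The strongest reply is that little depends on this. No hypotheses are tested (Section 10.1), the affected endpoints are secondary or exploratory and descriptive, and engraftment is not shown to be touched. Abstinence and barrier methods qualify at once, so nobody needs a new hormonal method to enter. Concomitant medication is reviewed at every visit, and Section 10.4.1 tabulates each subject at each time point and plots individual trajectories for the secondary and exploratory endpoints. In a trial of 10, an affected subject would be visible. All of this stands. It keeps the point minor and removes any need for a separate flagging procedure, but it does not explain why two of the named hormonal products escape a condition that the sponsor applies to others.

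Four stronger readings are tempting and should not be drawn.

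- *The stability rule cannot be checked.* Section 8.1 says "all therapies and medication taken up to 2 months prior to the Screening Visit should be recorded", and a reader might subtract 2 months from 3 and infer that 1 month is unverifiable. That window decides which therapies are listed, not how far back their start dates go. A method in current use falls inside it, and Section 11.1.11 requires source records to hold start and end dates, dose changes and documentation of eligibility.
- *A new method is known to change these endpoints.* The documents name hormonal dysregulation as a cause of acne. They give no direction, size or onset for the effect of any contraceptive on IGA, lesions or sebum.
- *One such subject would halt escalation.* That takes 2 DLTs, and the definition already sets aside events with another clear cause.
- *A hormonal IUD is an equally clear case.* The type is not stated, and Exclusion 14 read literally could bar any IUD.

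The 3-month period itself reaches injectables and rings only by analogy with the routes already covered. That is a fair criticism. The request is for consistency with the sponsor's own rule, not for a period that the documents justify independently.

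**Conclusion.** The point holds as a minor wording gap with a cheap remedy. As written, a subject who starts Depo-Provera or NuvaRing 5 to 7 days before NB01 is eligible, while one who starts an oral contraceptive or implant then is not. In an uncontrolled study with 5 subjects per cohort, this leaves open an avoidable possible confounder of the descriptive IGA, lesion-count and sebum changes, and some ambiguity in attributing an IGA-based DLT.

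The conclusion assumes that at least one such subject enrolls, which the documents neither predict nor rule out. It also relies on the protocol's own view that hormonal state bears on acne. It does not assume that a newly started method has a measurable effect within 7 or 28 days; the documents are silent on that.

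**What to change.** Reword Inclusion 7 and Section 5.3 in the same terms, so that the stability requirement already in the protocol applies to every hormonal method the criterion accepts, with no planned change of method through Day 28. Leave non-hormonal methods open to new starters. If the sponsor means to exempt the injectable and the ring, give the reason in the text.

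Separately, reconcile Inclusion 7, which accepts IUDs and implants, with Exclusion 14, which read literally could exclude them, and state whether the accepted IUD includes hormonal types. Which way that is settled is for the sponsor.

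The cost is one matched edit in two places plus the reconciliation. A few recent starters would be delayed or become ineligible. No change to the medication look-back and no extra data collection is needed.
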